5.3.3. Data Handling

Unless otherwise specified, data handling rules specified in Section 5.1.3 will be applied to the major secondary analyses.

5.4. Other Efficacy Variable(s)

Other secondary efficacy endpoints include the endpoints related to

- PASI
- IGA

5.4.1. Definition

Refer to Section 5.1.2 for the definitions of the other efficacy endpoints described in the following section.

5.4.2. Analysis Methods

Most of the other secondary efficacy analyses described in this section will be performed using the full analysis set. For the other secondary analyses, all non-inferiority tests will be performed 1-sided ($\alpha=0.025$) with a non-inferiority margin of 10%. The margin of 10% was similarly determined as for the primary endpoint. All the non-inferiority analyses will also be repeated for the per protocol population (Section 2.4.1.2). All superiority statistical testing will be performed 2-sided ($\alpha=0.05$). Nominal p-values will be presented. The same statistical methods used for the primary endpoint will also be used to analyze the secondary endpoints.

5.4.2.1. Analyses Related to IGA

- The non-inferiority test comparing guselkumab with secukinumab for the proportion of subjects achieving an IGA score of cleared (0) or minimal (1) at Week 16 will be performed.
- The non-inferiority test comparing guselkumab with secukinumab for the proportion of subjects achieving an IGA score of cleared (0) or minimal (1) at Week 12 will be performed.
- The proportions of subjects who achieve an IGA score of cleared (0) response, IGA score of cleared (0) or minimal (1) response, and IGA score of mild or better (≤ 2) response over time through Week 56 will be summarized by treatment group. Line plots will be provided displaying the proportions and 95% CIs of subjects achieve an IGA score of cleared (0); and an IGA score of cleared (0) or minimal (1) through Week 48. The 95% CI will be calculated based on normal approximation.
- The proportions of subjects achieving an IGA score of cleared (0) response, IGA score of cleared (0) or minimal (1) response, and IGA score of mild or better (≤ 2) response will also be summarized over time through Week through Week 56 by treatment group using observed data after applying treatment failure rules.

5.4.2.2. Analyses Related to PASI

- The non-inferiority test comparing guselkumab with secukinumab for the proportion of subjects achieving a PASI 90 response at both Week 16 and Week 48 will be performed. If non-inferiority is established, the superiority test on this endpoint will be performed.
- The non-inferiority test comparing guselkumab with secukinumab for the proportion of subjects achieving a PASI 75 response at Week 16 will be performed.
- The non-inferiority test comparing guselkumab with secukinumab for the proportion of subjects achieving a PASI 90 response at Week 16 will be performed.
- The non-inferiority test comparing guselkumab with secukinumab for the proportion of subjects achieving a PASI 90 response at all 7 visits from Week 24 through Week 48 will be performed. If non-inferiority is established, the superiority test on this endpoint will be performed.

- The proportions of subjects who achieve a PASI 75 response at Week 48 among PASI 75 responders at Week 12 will be summarized by treatment group.
- The proportions of subjects who achieve a PASI 90 response at Week 48 among PASI 90 responders at Week 16 will be summarized by treatment group.
- The proportions of PASI 100 responders, PASI 90 responders, PASI 75 responders, and PASI 50 responders will be summarized over time through Week 56 by treatment group. Line plots will be provided displaying proportions and 95% CIs of PASI 100 responders and PASI 90 responders through Week 48. The 95% CI will be calculated based on normal approximation.
- The proportions of PASI 100 responders, PASI 90 responders, PASI 75 responders, and PASI 50 responders, will be summarized over time through Week 56 by treatment group using observed data after applying treatment failure rules.
- The percent improvement from baseline in PASI will be summarized over time through Week 56 by treatment group.
- The proportion of subjects who achieve 100% improvement, $\geq 90\%$, $\geq 75\%$, or $\geq 50\%$ improvement from baseline in PASI component (induration, erythema, and scaling) and region component (head, trunk, upper extremities, and lower extremities) will be summarized at Week 48 by treatment group.

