1.4. Sample Size Justification

This study is designed to evaluate the efficacy of guselkumab 100 mg vs secukinumab 300 mg. The power and sample size were evaluated for the primary endpoint of PASI 90 at Week 48. In addition, since the response rate for guselkumab for PASI 100 at Week 48 is around 50% where the variability is the highest, the power and sample size were also evaluated for this major secondary endpoint. The assumptions for the sample size and power calculations were based on the data from the guselkumab CNTO1959PSO3001 and CNTO1959PSO3002 and the secukinumab Phase 3 studies (ERASURE and FIXTURE).¹ The assumptions used are as follows:

- The proportion of subjects who achieve a PASI 90 response at Week 48 is 70% to 80% in subjects receiving guselkumab and 60% to 70% for subjects receiving secukinumab.
- The proportion of subjects who achieve a PASI 100 response at Week 48 is 44% to 51% in subjects receiving guselkumab and 35% to 40% for subjects receiving secukinumab.

Approximately 1,040 subjects are planned to be randomized in a 1:1 ratio to either guselkumab 100 mg (n=520) (administered at Weeks 0, 4, 12 and q8w thereafter until Week 44) or secukinumab 300 mg (n=520) (administered at Weeks 0, 1, 2, 3, and 4 and q4w thereafter until Week 44).

Based on the above assumptions, the planned sample size, and a noninferiority margin of 10%, the power to demonstrate the non-inferiority for the primary endpoint of PASI 90 at Week 48 and the major secondary endpoint of PASI 100 at Week 48 will be > 99%.

Table 1 provides the power for detecting a treatment difference (superiority of guselkumab over secukinumab) under varying assumptions at a significance level of 0.05 for the primary endpoint PASI 90 at Week 48 and the major secondary endpoint of PASI 100 at Week 48.

Table 1: Power to Detect a Treatment Effect Based on Different Proportions of Subjects Achieving the Primary Endpoint PASI 90 at Week 48 and the Major Secondary Endpoint PASI 100 at Week 48

Secukinumab 300 mg (n=520)	Primary Endpoint PASI 90 at Week 48	
	Guselkumab 100 mg (n=520)	
60%	70%	92%
	75%	>99%
	75%	94%
65%	80%	>99%
	80%	96%
70%	Selected Major Secondary Endpoint PASI 100 at Week 48	
	44%	84%
	45%	91%
	46%	95%
	49%	83%
40%	50%	90%
	51%	95%

PASI = Psoriasis Area and Severity Index.

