2.5. Definition of Subgroups

To evaluate the consistency of efficacy based on demographic characteristics, baseline disease characteristics, and psoriasis medication history, subgroup analyses will be performed for the primary endpoint, PASI 90, and the major secondary endpoints of PASI 100 and IGA score of cleared (0), all assessed at Week 48. The subgroups for subgroup analyses include the following:

Baseline demographics:

- Sex (male, female)
- Race
- Baseline Age (<45 years, 45 to <65 years, ≥65 years)
- Baseline weight (≤90 kg, >90 kg)
- BMI (Normal [<25], Overweight [25 -<30], Obese [≥30])

Baseline disease characteristics:

- Age at diagnosis (years) (<25, ≥25)
- Psoriasis disease duration (years) (<15, ≥15)
- Baseline PASI (<20, ≥20)
- Baseline IGA (<4, =4)

- Baseline BSA (<20%, ≥20%)
- Psoriatic arthritis (Yes, No)

Psoriasis medication history:

- Phototherapy (ultraviolet B light [UVB] or psoralen and ultraviolet A light therapy [PUVA])
 - Never used
 - Ever used
- Non-biologic systemics (PUVA, MTX, cyclosporine, acitretin, apremilast, or tofacitinib)
 - Never used
 - Ever Used
- Biologics (etanercept, infliximab, alefacept, efalizumab, ustekinumab, briakinumab, ixekizumab, brodalumab, adalimumab, tildrakizumab, or risankizumab)
 - Never used
 - Ever Used
- Non-biologic systemics or biologics (as defined above)
 - Never used
 - Ever used
- Anti-TNF α agent (etanercept, infliximab, adalimumab)
 - Never used
 - Ever used
- IL-12/23 inhibitors (ustekinumab, briakinumab, tildrakizumab, or risankizumab)
 - Never used
 - Ever used
- IL-17 inhibitors (ixekizumab, or brodalumab)
 - Never used
 - Ever used
- Subjects who had an inadequate response to, were intolerant to, or had a contraindication to any of the following four biologic therapies: etanercept, infliximab, adalimumab or ustekinumab

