5.1. Analysis Specifications

5.1.1. Level of Significance

All statistical procedures to test superiority hypotheses will be performed at a 2-sided significance level of 0.05 and 1-sided at a significance level of 0.025 for non-inferiority. This study is designed to maintain an overall Type I error of 0.05 or less for the primary analysis and major secondary analyses. Nominal p-values will be reported for other secondary analyses.

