5.2.6. Subgroup Analysis

For each of the subgroups defined in Section 2.5, the proportion of subjects achieving a PASI 90 response at Week 48 by treatment group will be summarized, respectively. Under the assumption of normal distributions, the 95% confidence interval without adjusting for investigator site of the difference between the guselkumab 100 mg and the secukinumab 300 mg groups for the primary endpoint will also be provided. In addition, the proportion of PASI 90 responders at Week 48 by investigator site will be summarized.

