5.3.2. Analysis Methods

The major secondary efficacy analyses described in this section will be performed using the full analysis set. For the major secondary analyses, all non-inferiority tests will be performed 1-sided ($\alpha=0.025$) with a non-inferiority margin of 10%. The margin of 10% was similarly determined as for the primary endpoint. All superiority statistical testing will be performed at a two-sided

significance level of 0.05. In addition, all the major secondary analyses will also be performed on the per protocol analysis set defined in Section 2.4.1.2. The same statistical methods used for the primary endpoint will also be used to analyze the major secondary endpoints. In addition, similar Sensitivity Analyses 1 and 2 as performed for the primary endpoint will be performed for the major secondary endpoints. For the Sensitivity Analysis 2 for the endpoints of PASI 75 response and PASI 90 response at Week 12 where non-inferiority test only is specified for these 2 endpoints, 1-side Wald test with Mantel-Haenszel weights adjusted by investigator site will be performed. The sensitivity analyses using MI will be performed similarly as that done for the primary endpoint including using the same seeds and same number of imputations.

In addition, subgroup analyses for the IGA score of cleared (0) at Week 48 and PASI 100 at Week 48 will be performed similarly as for the primary endpoint.

The major secondary analyses are:

- The non-inferiority test comparing guselkumab with secukinumab for the proportion of subjects achieving a PASI 75 response at both Week 12 and Week 48 will be performed. If non-inferiority is established, the superiority test on this endpoint will be performed.
- The non-inferiority test comparing guselkumab with secukinumab for the proportion of subjects achieving a PASI 90 response at Week 12 will be performed.
- The non-inferiority test comparing guselkumab with secukinumab for the proportion of subjects achieving a PASI 75 response at Week 12 will be performed.
- The non-inferiority test comparing guselkumab with secukinumab for the proportion of subjects achieving a PASI 100 response at Week 48 will be performed. If non-inferiority is established, the superiority test on this endpoint will be performed.

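### Subgroup differences get normal-theory intervals with no minimum size or sparse-cell rule, so very small strata can undercover or show zero width; the early responder plots share the flaw, with little visible effect.

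*SAP*

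**What the plan says.** **Subgroups.** SAP 5.2.6 sets the method for PASI 90 at Week 48: "Under the assumption of normal distributions, the 95% confidence interval without adjusting for investigator site of the difference" between arms. SAP 5.3.2 carries it to two further endpoints: "subgroup analyses for the IGA score of cleared (0) at Week 48 and PASI 100 at Week 48 will be performed similarly" to the primary endpoint. SAP 2.5 lists the strata. One is prior use of "IL-17 inhibitors (ixekizumab, or brodalumab"). Another is race, with no levels given there and no rule for collapsing them; SAP Table 2 has nine race categories. No minimum stratum size is set.

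**Plots.** SAP 5.4.2.2 states: "Line plots will be provided displaying proportions and 95% CIs of PASI 100 responders and PASI 90 responders through Week 48". The interval is specified as "The 95% CI will be calculated based on normal approximation". SAP 5.4.2.1 uses the same sentence for IGA 0 and IGA 0/1. The first plotted visit is not stated. The protocol's Time and Events Schedule has PASI and IGA assessed at every visit from Week 0, including Weeks 1, 2 and 3.

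Neither section writes out a formula or says what to do when an arm has no responders or only responders.

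**The concern.** The usual normal-approximation (Wald) interval estimates its standard error from the observed proportion. When that proportion is 0% or 100%, the estimated standard error is zero and the interval becomes a point. Close to those limits, the interval is too short and can run outside 0-100%.

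Small strata are foreseeable. Protocol 4.2 excludes anyone who has had secukinumab (criterion 12) and anyone who received another IL-17-targeted agent within 6 months (criterion 16). The prior IL-17 stratum is therefore limited to earlier users of two named drugs. Some race categories may also be small. The subgroup intervals exist to judge whether the effect is consistent. A stratum in which every subject in both arms responds would be reported as a difference of 0 with limits of 0 and 0, which is false certainty where there is least information.

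The plots raise the same issue on a smaller scale. PASI 100 and IGA 0 both mean complete clearance, and every eligible subject starts with PASI of at least 12 and IGA of at least 3, so very low rates in the first weeks are plausible.

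**Working it through.** **Inputs from the documents**
- Size: "Approximately 1,040 subjects are planned to be randomized in a 1:1 ratio to either guselkumab 100 mg (n=520"), and 520 on secukinumab (SAP 1.4).
- Week 48 PASI 90: "The proportion of subjects who achieve a PASI 90 response at Week 48 is 70% to 80% in subjects receiving guselkumab" and 60-70% on secukinumab. PASI 100: 44-51% and 35-40% (SAP 1.4). No planning rate is given for IGA 0.
- Plot denominator: the full arm, about 520, because missing counts as non-response (SAP 5.1.3.3).

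**Assumptions.** Stratum sizes and response rates at early visits are not in the documents, so both are shown as ranges. The normal approximation is read as Wald.

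**Step 1. The plan's own figure.** The SAP states no coverage figure. Its Table 1 powers check the sample size and rates:

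power = Φ{[Δ − 1.96·√(2p̄(1−p̄)/n)] / √[(p₁(1−p₁)+p₂(1−p₂))/n]}

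For 70% v 60%: (0.10 − 1.96×0.02958)/0.02942 = 1.43, giving 92.3% (stated 92%). The other numeric cells give 94.2 and 96.2% for PASI 90, and 84.5, 91.0, 95.2, 83.3, 90.1 and 94.7% for PASI 100. All are within 0.5 points of Table 1.

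**Step 2. Subgroup differences.** Wald interval: d ± 1.96·√[p̂₁(1−p̂₁)/m + p̂₂(1−p̂₂)/m], with m per arm. Coverage comes from exact binomial enumeration.

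| m per arm | PASI 90 rates | Wald coverage | Newcombe coverage | P(zero width) |
|---|---|---|---|---|
| 5 | 70 v 60 | 85.3% | 96.0% | 1.5% |
| 5 | 75 v 65 | 84.6% | 96.8% | 2.9% |
| 5 | 80 v 70 | 83.2% | 97.7% | 5.6% |
| 10 | same three pairs | 91.2-91.7% | 95.3-95.5% | at most 0.3% |
| 15 | same three pairs | 93.4-93.6% | 94.6-95.5% | practically nil |
| 20 | same three pairs | 93.6-94.2% | 94.5-95.1% | practically nil |

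Zero width needs each arm to be all responders or all non-responders. For 80 v 70 with 5 per arm: (0.8⁵+0.2⁵)(0.7⁵+0.3⁵) = 0.328×0.1705 = 0.056.

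Over every pair in the PASI 90 planning ranges, not only those 10 points apart, minimum/mean Wald coverage is 79/85% at 5 per arm, 90/92% at 10, 92/93% at 15 and 93/93.5% at 20. For PASI 100, 10 per arm gives 89/92%.

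Example with 5/5 v 5/5:
- Wald gives [0, 0].
- Newcombe: the Wilson lower limit for 5/5 is 5/(5+3.84) = 0.566, so the interval is ±43.4 points.
- Miettinen-Nurminen: solve 4.5·δ/(1−δ) = 3.84, so δ = 0.46 and the interval is ±46 points.

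**Step 3. Plots, n = 520.** Wald: p̂ ± 1.96·√(p̂(1−p̂)/n).

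| Responders | Wald | Wilson |
|---|---|---|
| 0 | [0, 0] | [0, 0.73%] |
| 1 | [−0.18%, 0.57%] | [0.03%, 1.08%] |
| 10 | [0.74%, 3.10%] | [1.05%, 3.50%] |

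The Wilson upper limit at zero is 3.84/523.84 = 0.73%. The Wald lower limit is negative for 1 to 3 responders. At 3 it is 0.577% − 1.96×0.332% = −0.07%; at 4 it is 0.769% − 1.96×0.383% = +0.02%.

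| Assumed true rate | Wald coverage | Wilson coverage |
|---|---|---|
| 0.1% | 40.5% | 90.4% |
| 0.2% | 64.6% | 97.9% |
| 0.5% | 92.5% | 95.1% |
| 0.6% | 81% | 96% |
| 1.0% | 88.5% | 95.6% |

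The probability of no responders is 0.999⁵²⁰ = 59% at a true rate of 0.1% and 0.998⁵²⁰ = 35% at 0.2%. Wald coverage below 90% occurs only up to a true rate of about 1.6% (about 8 of 520). From 5% upward it is about 93% or more.

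**The case against.** The strongest reply is that nothing depends on these intervals. The confirmatory tests are the Mantel-Haenszel-weighted Z-test and the CMH test (SAP 5.2.3). The plots describe each arm separately, other secondary analyses carry nominal p-values (SAP 5.1.1), and no decision rule uses a subgroup interval. That stands, and it makes this a minor point.

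A second reply is that the sizes and rates that cause trouble are assumed. That also stands. With about 520 per arm, two-level splits such as sex, weight or baseline PASI should far exceed 20 per arm, and only a few rare strata are at risk.

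A third reply is that the SAP does not say Wald, and a score interval would not collapse at zero. This is true, but Wald is the natural reading of both sentences, and the ambiguity is itself a reason to name the method.

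A reader might infer more than the documents support:
- **That the error bars and subgroup intervals will be wrong.** No early response rates or stratum sizes are given, so the fault is conditional.
- **That response near 100% makes collapse common.** With 5 per arm and 90% v 80%, coverage falls to 74% and the zero-width probability rises to 19%. Those rates lie above the plan's PASI 90 ranges, and at the plan's rates the figures are 83-85% and 1.5-6%.
- **That a zero-width bar at Week 0 is an error.** Response is 0% there by construction, so such a bar would be correct.

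**Conclusion.** The point holds in a limited form. The SAP prescribes normal-theory intervals for subgroup differences without a size or sparse-cell rule, while listing strata that could be very small. Taking Wald as the method and the plan's PASI 90 rates, the shortfall matters at about 5 per arm, is modest at 10, and is negligible from about 15-20.

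The plots share the flaw if true rates fall below about 1.6%. That is plausible for PASI 100 and IGA 0 in the first weeks, but it is not documented. Even then the limits are off by at most about 0.7 percentage points, hardly visible on a 0-100% axis.

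No primary or major secondary conclusion changes. This is a worthwhile tidy-up and does not threaten the trial's inference.

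**What to change.** - **SAP 5.2.6** (and through it the subgroup analyses in 5.3.2): name the Miettinen-Nurminen score interval, already SAP reference 2, or the Newcombe interval for unadjusted subgroup differences.
- **SAP 5.4.2.1 and 5.4.2.2**: name the Wilson interval for the plotted proportions.

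This changes three sentences and a programming option. It should be done before the Week 56 database lock. The SAP amendment history says enrollment is complete, so stratum counts pooled over arms could be checked without unblinding to see whether any are small.

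The cost is a small inconsistency. SAP 5.2.3 gives the overall difference a normal-approximation interval with Mantel-Haenszel weights, so subgroup and overall intervals shown together would use different methods. A footnote would cover this, and in large strata the two methods agree closely: with 100 per arm at the three PASI 90 pairs, Wald coverage is 94.7% and Newcombe 94.9-95.0%.

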5.4.3. Data Handling

Data handling rules specified in Section 5.1.3 will be applied to all IGA related and PASI related analyses.

6. SAFETY

Safety will be assessed by summarizing the incidence and type of AEs and examining changes in laboratory parameters (hematology and chemistry), vital signs and electrocardiogram (ECG) parameters, and suicidal ideation and behavior as measured by the eC-SSRS (electronic Columbia-Suicide Severity Rating Scale).

In all the safety analysis, subjects who were randomized and received at least 1 (partial or complete) dose of study agent will be included and analyzed according to the treatment they actually received, regardless of the treatment they are randomized to. No formal hypothesis testing is planned.

Depending on the safety data categories, the cumulative safety data will be analyzed through Week 56. Unless otherwise specified, tabular summaries of safety events for the study periods are presented as follows:

- Guselkumab 100 mg
- Secukinumab 300 mg

This allows between-group comparisons of safety between the guselkumab 100 mg group and the secukinumab 300 mg group based on the same follow-up period in each group.

6.1. Adverse Events

The verbatim terms used in the CRF by investigators to identify adverse events will be coded using the Medical Dictionary for Regulatory Activities (MedDRA). Any AE starting at or after the initial administration of study agent through the end of the trial is considered to be treatment emergent. If the event occurs on the day of the initial administration of study agent, and either event time or time of administration are missing, then the event will be assumed to be treatment emergent. If the event date is recorded as partial or completely missing, then the event will be considered to be treatment emergent unless it is known to be prior to the first administration of study agent based on partial onset date or resolution date. All reported treatment-emergent adverse events will be included in the analysis. For each adverse event, the number and percentage of subjects who experience at least 1 occurrence of the given event will be summarized by treatment group. In addition, event rate per 100 subject-years of follow-up for serious infections will be provided.

Summary tables will be provided for:

- AEs
- Serious AEs (SAEs)
- AEs leading to discontinuation of study agent administration
- AEs by severity
- AEs by relationship to study agent
- Infections
- Serious infections
- Infections treated with oral or parenteral antimicrobial treatment parenteral antibiotics
- Injection-site reactions
- AEs of psoriasis

In addition to the summary tables, listings will be provided for subjects who:

- Had SAEs
- Had AEs leading to discontinuation of study agent administration
- Had AEs of severe intensity
- Had serum sickness-like reactions or anaphylactic reactions

Any unfavorable or unintended sign that occurs at the injection site is an injection site reaction and will be recorded as an injection site reaction by the investigator on the eCRF. An infection is defined as any AE that was recorded as an infection by the investigator on the eCRF.

The treatment-emergent adverse events of psoriasis include any event of erythrodermic psoriasis, pustular psoriasis, guttate psoriasis, and worsening or exacerbation of psoriasis. Incidence of these events will be summarized.

Since safety should be assessed relative to exposure and follow-up, most AE summary tables will include average weeks of follow-up and average number of study agent administrations for each treatment group.

